10.1.2 Solicited Adverse Events

The occurrence of selected indicators of safety as listed in [Table 10.a](#) will be measured/collected for 7 days (solicited local [injection site] AEs) and 14 days (solicited systemic AEs) following administration of each trial vaccine dose (including the day of administration) and will be recorded on the “Local and Systemic AEs” eCRF, as applicable. These will be summarized in the final report under the category “solicited AEs” to differentiate them from other AEs which were not solicited. Any solicited local or systemic AE observed as continuing 8 days and 15 days, respectively, following each trial vaccination will be recorded as an unsolicited AE on the “AE” eCRF.

Table 10.a Solicited Local and Systemic Adverse Events

Solicited local (injection site) AEs:	Pain Erythema Swelling
Solicited systemic AEs:	Fever ^(a) Headache Asthenia Malaise Myalgia

(a) Fever is defined as greater than or equal to 38°C (100.4°F) regardless of method taken [[15](#)].

The severity of solicited safety parameters will be assessed as described in [Table 10.b](#).

Table 10.b Severity Scales for Solicited Safety Parameters

Adverse Event	Severity grade	Severity
Pain at injection site	0	None
	1	Mild: No interference with daily activity
	2	Moderate: Interference with daily activity with or without treatment
	3	Severe: Prevents daily activity with or without treatment
Erythema at injection site ^(a)	0	<25 mm
	1	Mild: $\geq 25 - \leq 50$ mm
	2	Moderate: $>50 - \leq 100$ mm
	3	Severe: >100 mm
Swelling at injection site ^(a)	0	<25 mm
	1	Mild: $\geq 25 - \leq 50$ mm
	2	Moderate: $>50 - \leq 100$ mm
	3	Severe: >100 mm
Headache	0	None
	1	Mild: No interference with daily activity
	2	Moderate: Interference with daily activity with or without treatment
	3	Severe: Prevents normal activity with or without treatment
Asthenia	0	None
	1	Mild: No interference with daily activity
	2	Moderate: Interference with daily activity
	3	Severe: Prevents daily activity
Malaise	0	None
	1	Mild: No interference with daily activity
	2	Moderate: Interference with daily activity
	3	Severe: Prevents daily activity
Myalgia	0	None
	1	Mild: No interference with daily activity
	2	Moderate: Interference with daily activity
	3	Severe: Prevents daily activity
Fever ^(b)	Record body temperature in °C/°F	

(a) Subjects are to record greatest surface diameter in mm on the diary card.

(b) Fever is defined as greater than or equal to 38°C (100.4°F) regardless of method taken [15].

10.1.3 Medically Attended Adverse Events

MAAEs are defined as AEs leading to a medical visit to or by a healthcare professional including visits to an emergency department, but not fulfilling seriousness criteria.

10.1.4 Serious Adverse Events

An SAE is defined as any untoward medical occurrence that:

1. Results in DEATH.
2. Is LIFE THREATENING.
 - The term “life threatening” refers to an event in which the subject was at risk of death at the time of the event; it does not refer to an event that hypothetically might have caused death if it were more severe.
3. Requires inpatient HOSPITALIZATION or prolongation of existing hospitalization.
4. Results in persistent or significant DISABILITY/INCAPACITY.
5. Leads to a CONGENITAL ANOMALY/BIRTH DEFECT in the offspring of a subject.
6. Is an IMPORTANT MEDICAL EVENT that satisfies any of the following:
 - May require intervention to prevent items 1 through 5 above.
 - May expose the subject to danger, even though the event is not immediately life threatening or fatal or does not result in hospitalization.

10.2 Causality of Adverse Events

Relatedness (causality) to vaccine will also be assessed by the Investigator. The relationship of each AE, including solicited systemic AEs (all solicited local [injection site] AEs are considered as related) to the trial vaccine will be assessed using the following categories:

Related:	There is suspicion that there is a relationship between the trial vaccine and the AE (without determining the extent of probability); there is a reasonable possibility that the trial vaccine contributed to the AE.
Not Related:	There is no suspicion that there is a relationship between the trial vaccine and the AE; there are other more likely causes and administration of the trial vaccine is not suspected to have contributed to the AE.

10.2.1 Relationship to Trial Procedures

Relationship (causality) to trial procedures should be determined for all AEs.

The relationship should be assessed as “Yes” if the Investigator considers that there is reasonable possibility that an event is due to a trial procedure. Otherwise, the relationship should be assessed as “No”.

10.2.2 Outcome of Adverse Events

Resolved: The subject has fully recovered from the event or the condition has returned to the level observed at Baseline.

Resolving: The event is improving but the subject is still not fully recovered.

Not resolved: The event is ongoing at the time of reporting and the subject has still not recovered.

Resolved with sequelae: As a result of the AE, the subject suffered persistent and significant disability/incapacity (eg, became blind, deaf or paralysed).

Fatal: The subject died due to the event. If the subject died due to other circumstances than the event, the outcome of the event per se should be stated otherwise (eg, not resolved or resolving).

Unknown: If outcome is not known or not reported.

10.3 Additional Points to Consider for Adverse Events

An untoward occurrence generally may:

- Indicate a new diagnosis or unexpected worsening of a pre-existing condition. Intermittent events for pre-existing conditions or underlying disease should not be considered as AEs.
- Necessitate therapeutic intervention.
- Require an invasive diagnostic procedure.
- Require vaccine discontinuation or a change in concomitant medication.
- Be considered unfavorable by the Investigator for any reason.

Diagnoses vs. signs and symptoms:

- Each event should be recorded to represent a single diagnosis. Accompanying signs (including abnormal laboratory values) or symptoms should NOT be recorded as additional AEs. If a diagnosis is unknown, signs or symptoms should be recorded appropriately as AEs.

Worsening of AEs:

- If the subject experiences a worsening or complication of an AE after starting administration of the trial vaccine, the worsening or complication should be recorded as a new AE. Investigators should ensure that the AE term recorded captures the change in the condition (eg, “worsening of...”).
- If the subject experiences a worsening or complication of an AE after any change in trial vaccine, the worsening or complication should be recorded as a new AE. Investigators should ensure that the AE term recorded captures the change in the condition (eg, “worsening of...”).

Changes in severity of AEs:

- If the subject experiences changes in severity of an AE, the event should be captured once with the maximum severity recorded.

Preplanned surgeries or procedures:

- Preplanned procedures (surgeries or therapies) that were scheduled prior to signing of informed consent form/assent form are not considered AEs. Complications resulting from any planned surgery should be reported as AEs.

Elective surgeries or procedures:

- Elective procedures performed where there is no change in the subject's medical condition should not be recorded as AEs, but should be documented in the subject's source documents. Complications resulting from an elective surgery should be reported as AEs.

10.4 Procedures

10.4.1 Collection and Reporting of Adverse Events

All AEs, whether considered related to the use of the trial vaccine or not, must be monitored until symptoms subside and any abnormal laboratory values have returned to Baseline, or until there is a satisfactory explanation for the changes observed, or until death, in which case a full pathologist's report should be supplied, if possible. All findings must be reported on an AE eCRF and on the SAE form, if necessary (see Section 10.4.2). All findings in subjects experiencing AEs must also be reported in the subject's source documents. Any unsolicited AEs for 28 days (day of vaccination+27 subsequent days) following each TDV/placebo dose will be collected during site visits by interview.

- The following information will be documented for each event:
- Reported term for the AE.
- Start and end date.
- Serious (Y/N).
- Severity.
- Investigator's opinion of the causality (relationship) between the event and administration of trial vaccines ("related" or "not related").
- Investigator's opinion of the causality (relationship) to trial procedure(s), including the details of the suspected procedure.
- Action taken with the trial treatment (trial vaccine).
- Outcome of event.

10.4.2 Collection and Reporting of Solicited Adverse Events

The occurrence of selected indicators of safety will be collected on diary cards by the subject/LAR for 7 days (solicited local [injection site] AEs) and 14 days (solicited systemic AEs) following administration of each trial vaccine dose (including the day of administration) and will be recorded on the “Local and Systemic AEs” eCRF, as appropriate. Any solicited local (injection site) or systemic AE observed as continuing 8 days and 15 days, respectively, following each trial dose administration, will be recorded as an unsolicited AE on the AE eCRF. Any solicited local (injection site) or systemic AE that resolved before 8 days and 15 days, respectively, following each trial dose administration, but which recurs at a later time (ie, if discontinues), will be recorded as an unsolicited AE on the AE eCRF.

Any solicited AE that meets any of the following criteria must be entered as an AE on the AE eCRF:

- Solicited local (injection site) or systemic AEs that lead the subject to withdraw from the trial.
- Solicited local (injection site) or systemic AEs that lead to the subject being withdrawn from the trial by the Investigator.
- Solicited local (injection site) and systemic AEs that otherwise meet the definition of an SAE (see Section 10.1.2).

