7.5 Criteria for Premature Discontinuation of Trial Vaccine Administration

Early termination of a subject's participation in the trial will by default prevent the subject from continued trial vaccine administration, as the subject will no longer be participating in the trial. In addition to early termination (see Section 7.4) criteria, other situations may apply in which subjects may continue participating in the trial (e.g., contributing safety data according to protocol) but trial vaccine administration is discontinued selectively. Regardless of the reasons for discontinuation of the trial vaccine administration, this must be documented as protocol deviation. Even if the subject is deemed ineligible to receive trial vaccine, all efforts should be made to continue the collection of safety data according to protocol. In addition, the primary reason for premature discontinuation of trial vaccine administration should be recorded in the eCRF ("end of trial vaccine administration" page) using the following categories:

1. Adverse Event: The subject has experienced an AE (irrespective of being related/unrelated to the trial vaccine or trial-related procedures) for which subsequent trial vaccine administrations impose an unacceptable risk to the subject's health, but the subject may continue trial participation for safety, or a subset of other trial procedures.
2. Lost to follow-up: The subject did not return to the clinic and at least 3 attempts to contact the subject (or subject's LAR) were unsuccessful. Attempts to contact the subject must be documented.
3. Withdrawal of consent: The subject (or subject's LAR) wishes to withdraw from the trial. The primary reason for early termination will be "withdrawal of consent" if the subject withdraws from participation due to a non-medical reason (i.e., reason other than AE). The reason for withdrawal, if provided, should be recorded in the eCRF.
4. Premature trial termination by the Sponsor, a regulatory agency, the IEC/IRB, or any other authority.

If the clinical trial is prematurely terminated by the Sponsor, the Investigator is to promptly inform the trial subjects and local IEC/IRB and should assure appropriate follow up for the subjects. The primary reason for early termination in this case will be "trial termination".

5. Subject's death during trial participation.

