10.4.3 Collection and Reporting of Medically Attended Adverse Events

MAAEs occurring from first vaccination at Day 1 (M0) until the end of the trial (Day 270 [M9]) will be collected during site visits by interview and must be recorded as an AE on the AE eCRF.

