13.1.4 Safety Analysis

Solicited AEs

In all subjects, the presence and severity (Grade) of solicited local (injection site) AEs (pain, erythema, and swelling) and solicited systemic AEs (fever, asthenia, malaise, headache and myalgia) will be collected for 7 days and 14 days, respectively, following administration of each trial dose (including the day of administration) via collection of diary cards.

For each solicited AE, the number and percentage of subjects with local (injection site) and systemic AEs will be summarized by trial group and event severity for each day after each vaccination (ie, Day 1 through Day 7 for local [injection site] AEs and Day 1 through Day 14 for systemic AEs), and overall. Summaries of first onset of each event and the number of days subjects reported experiencing each event will also be provided. For subjects with more than 1 episode of the same event, the maximum severity will be used for tabulations.

Unsolicited AEs

Unsolicited AEs will be assessed for 28 days following administration of each trial dose (day of administration+27 subsequent days).

In all subjects, unsolicited AEs will be coded using the MedDRA, and summarized by SOC and PT for each trial group. AEs leading to trial or trial dose discontinuation or withdrawal will also be summarized.

Unsolicited AEs will be summarized as follows: by PT including events with frequency greater than a pre-defined frequency (the percentage will be specified in the SAP); by SOC and PT; by SOC, PT, and severity; and by SOC, PT, and relationship to the trial dose. Subjects reporting more than 1 occurrence for the term (level) being summarized will be counted only once.

MAAEs

In all subjects, MAAEs will be collected throughout the trial. MAAEs will be coded using MedDRA, and summarized by SOC and PT for each trial group.

SAEs

In all subjects, SAEs will be collected throughout the trial. SAEs will be coded using MedDRA, and summarized by SOC and PT for each trial group.

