In general, the number of events, number of subjects, and the percentage of subjects will be tabulated by trial group at each of the following levels: overall summary (any AEs/subjects with any AEs) and by SOC and PT. Subjects reporting more than 1 occurrence for the term (level) being summarized will be counted only once in the number/percentage of subjects. Percentages will be based on the number of subjects in the Safety Set who received the respective trial dose.

Unsolicited AEs up to 28 days post-vaccination will be summarized as follows:

- By SOC and PT;
- By SOC and PT including events with frequency greater than 2% in any trial group;
- By SOC and PT including non-serious events with frequency greater than 2% in any trial group (including a separate group of subjects who received different IPs at first and second vaccination [if any]);
- By SOC and PT for IP related events;
- By SOC and PT for IP related events with frequency greater than 2% in any trial group;
- By SOC, PT, and severity (mild, moderate, severe).

MAAEs post-vaccination throughout the trial duration will be summarized as follows:

- By SOC and PT;
- By SOC and PT for IP related events;
- By SOC, PT, and severity (mild, moderate, severe).

SAEs post-vaccination throughout the trial duration will be summarized as follows:

- By SOC and PT (including a separate group of subjects who received different IPs at first and second vaccination [if any]);
- By SOC and PT for IP related events.

AEs leading to IP withdrawal or trial discontinuation post-vaccination throughout the trial duration will be summarized as follows:

- By SOC and PT (including a separate group of subjects who received different IPs at first and second vaccination [if any]);

- By SOC and PT for IP related events.

In addition, overview tables by trial group will be generated for unsolicited AEs (collected up to 28 days post-vaccination), SAEs, MAAEs and AEs leading to IP withdrawal or trial discontinuation including the variables as outlined in [Table 7.d](#).

Table 7.d Overview of Unsolicited Adverse Events

	All AEs (28 days post- vaccination)	SAEs	MAAEs	AEs leading to IP withdrawal and/or trial discontinuation
Relationship to IP	✓	✓	✓	✓
Relationship to trial procedure	✓	✓	✓	✓
Severity	✓	✓	✓	✓
AEs leading to IP withdrawal and/or trial discontinuation	✓	✓	✓	
AEs leading to IP withdrawal	✓	✓	✓	✓
AEs leading to trial discontinuation	✓	✓	✓	✓
MAAEs	✓			✓
SAEs and Non-serious AEs	✓			✓
Deaths	✓	✓		✓

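### Protocol 10.4.2 has no AE eCRF trigger for a solicited reaction that stops dose 2 only, and SAP 7.11.1 read literally drops prolonged solicited AEs from the MAAE and IP-withdrawal tables

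*Protocol*

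**What the plan says.** **Recording.** Under protocol 10.4.2, solicited events in the 7-day (local) or 14-day (systemic) window go on the 'Local and Systemic AEs' eCRF. Events that continue past the window, or that resolve and later recur, also go on the AE eCRF, as unsolicited AEs. A list then follows, opening "Any solicited AE that meets any of the following criteria must be entered as an AE on the AE eCRF". Its three items are:

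- "Solicited local (injection site) or systemic AEs that lead the subject to withdraw from the trial";
- events after which the Investigator takes the subject out of the trial;
- solicited AEs that otherwise meet the SAE definition.

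**Stopping vaccine only.** Protocol 7.5 separates stopping trial vaccine from leaving the trial. Its item 1 covers an AE "for which subsequent trial vaccine administrations impose an unacceptable risk" to the subject's health, while the subject may stay in follow-up. The primary reason goes on a separate eCRF page for the end of vaccine administration.

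**Medical visits.** Protocol 10.4.3 says that MAAEs from first vaccination to Day 270 "must be recorded as an AE on the AE eCRF". The definition in 10.1.3 does not exclude solicited events.

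**Analysis.** Protocol 13.1.4, under its unsolicited AE heading, says "AEs leading to trial or trial dose discontinuation or withdrawal will also be summarized". SAP 7.11.1, also under its unsolicited AE heading, says "AEs leading to IP withdrawal or trial discontinuation post-vaccination throughout the trial duration will be summarized as follows": by SOC and PT, and again for IP-related events. The same section says that prolonged solicited AEs are captured on the AE CRF with a flag, shown in separate listings, and left out of all unsolicited AE summaries and listings.

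**The concern.** Both documents plan a table of AEs that cost a subject a dose. With two doses, only an event after dose 1 can do that, so a reaction to dose 1 is a natural way into the table. Yet the list that a site would consult for solicited events has no trigger for it. The AE eCRF is where 10.4.1 documents the action taken with trial vaccine. The documents do not say that the solicited-event form carries that field. A reaction held only on the solicited form may therefore never be linked to the missed dose.

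The SAP raises a second, separate problem. An event can be entered correctly on the AE eCRF and still be removed at the tabulation stage because it is a prolonged solicited AE. That would affect the IP-withdrawal table and also the MAAE table, which reports a named secondary safety endpoint (protocol 5.2.2).

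**Working it through.** The plan states no figure on this point to reproduce. The check is a comparison of texts, followed by a calculation of scale.

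**Step 1. A reaction that resolves in its window and stops dose 2, with the subject staying in the trial.**

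| Rule | Does it expressly require AE eCRF entry? |
|---|---|
| 10.4.2, continuing or recurring events | No: the event resolved in its window and did not recur |
| 10.4.2 list, items 1 and 2 | No: the subject has not left the trial |
| 10.4.2 list, item 3 | No, unless serious |
| 10.4.3 (MAAE) | Only if there was a medical visit |
| Footnote (o) of the schedule; 9.3.3; 9.3.4 | Not expressly: they name discontinuation or withdrawal of the subject, not of the dose |
| 10.4.1 | Only in general terms (all findings) |
| SAP 7.11.1 | No: it says that AEs leading to IP withdrawal are collected from the first dose, but names no form for solicited ones |

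The stop itself is recorded under 7.5, and SAP 7.3 tabulates its primary reason. The documents show that page as giving a reason category, such as adverse event. They do not say that it carries a coded term or relatedness, which the SAP 7.11.1 tables need.

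**Step 2. A non-serious solicited event with a medical visit.** 10.1.3 makes it an MAAE and 10.4.3 makes AE eCRF entry mandatory. Nothing in 10.4.2 contradicts this, so recording is covered.

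**Step 3. A prolonged solicited event with a medical visit or a stopped dose.** Protocol 10.4.2 sends it to the AE eCRF as an unsolicited AE. SAP 7.11.1 then bars prolonged solicited AEs from all unsolicited summaries. The MAAE and IP-withdrawal tables stand under that heading, and their overview, Table 7.d, is titled as an overview of unsolicited AEs. No exception is stated, so on a literal reading the event is left out of both tables.

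**Step 4. Scale.** Inputs: planned group sizes of 300 and 100 (protocol 6.1). One missed subject changes a percentage by 100/n:

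- TDV: 100/300 = 0.33 points
- Placebo: 100/100 = 1.00 point

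The documents give no rate of dose-2 stops due to a solicited AE. Assume 0.2% to 2% in the TDV group. The expected number of such subjects is 300 × p, and the chance of at least one is 1 − (1 − p)^300:

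| Assumed p | Expected subjects (TDV) | Chance of at least one |
|---|---|---|
| 0.2% | 0.6 | 45.2% |
| 0.5% | 1.5 | 77.8% |
| 1% | 3.0 | 95.1% |
| 2% | 6.0 | 99.8% |

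This is the chance that such a case arises, not the chance that it is missed.

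**The case against.** The strongest reply is that the text permits an omission but does not force one. The list in 10.4.2 makes entry mandatory for certain events and nowhere says that others stay off the form. The section itself sends continuing and recurring events to the AE eCRF outside the list. 10.4.1 asks for all findings there and for the action taken with vaccine. 10.3 names vaccine discontinuation among the features of an untoward occurrence. Every vaccine stop must be documented as a protocol deviation under 7.5. The reaction also remains in the solicited tables by severity and day, so no safety event disappears from the report. The hypersensitivity reactions that 7.3 names as contraindications to dose 2 are not solicited terms. Detailed form routing may sit in the Data Management Plan, which is not available here.

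Most of this stands, and it limits the claim to events that may be absent. It does not close the gap. Read literally, 10.4.1 would put every solicited event on the AE eCRF and leave the list with no purpose. Disposition and the solicited tables do not show which coded event cost the dose, and that is what the planned table is for. None of these replies addresses the SAP exclusion of prolonged events, which acts after correct entry.

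A reader might also infer that 10.4.2 and 10.4.3 conflict and that medically attended solicited reactions inside the window are lost from the MAAE endpoint. The documents do not support this. The two entry rules add to each other, and 10.4.3 alone suffices. At most, a site using 10.4.2 as its only checklist could overlook 10.4.3, which a cross-reference would prevent.

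**Conclusion.** The point holds in two limited parts.

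1. **Recording.** A solicited reaction that resolves in its window and stops dose 2, with the subject staying in the trial, has no express route to the AE eCRF. It may be absent from the IP-withdrawal tables, although the stop is visible in disposition.
2. **Tabulation.** Read literally, SAP 7.11.1 omits prolonged solicited AEs from the MAAE and IP-withdrawal tables even when they qualify and are correctly entered.

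The size is 0.33 points (TDV) or 1 point (placebo) per missed subject, at the planned group sizes. The number of such subjects is unknown; the range in the working rests on assumed rates.

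A reader might infer that the gap flatters TDV. An omission can only lower the count in the arm where it occurs, but the recording rules are the same in both arms, investigators are blinded, and no event rates by arm are given. No direction of bias between arms is shown. The trial is descriptive, so no hypothesis test is affected. What is at stake is the completeness of two safety tables.

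**What to change.** In protocol 10.4.2 and the matching eCRF instructions:

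- add a recording trigger for solicited AEs that lead to discontinuation of trial vaccine administration, with reference to 7.5;
- add a cross-reference to 10.4.3 for medically attended solicited AEs;
- in the same edit, correct the SAE cross-reference, which points to 10.1.2 although SAEs are defined in 10.1.4.

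In SAP 7.11.1, state that any AE meeting the MAAE or IP-withdrawal definition enters those tables whether or not the term was solicited or prolonged.

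These changes concern recording and tabulation only; they leave the rules on who receives dose 2 as they are. The cost is one trigger, one cross-reference and one SAP sentence. The downside is that a few events will appear in both the solicited tables and the MAAE or IP-withdrawal tables, which a table footnote can explain.
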